6.3. Permanent Discontinuation from Study Treatment

Subjects will receive study treatment until disease progression, death or unacceptable toxicity, including meeting stopping criteria for liver chemistry defined in Section 4.7.1. The investigator may discuss with a GSK Medical Monitor continuing a subject who is receiving benefit but has met the criteria for disease progression, if the following criteria are met: Investigator-determined clinical benefit (e.g. symptomatic improvement), lack of

significant toxicity (no drug related non-hematologic grade 3/4 AEs within the last 4 weeks) and no therapeutic alternatives expected to provide durable responses.

In addition, study treatment may be permanently discontinued for any of the following reasons:

- Deviation(s) from the protocol
- Request of the subject or proxy (withdrawal of consent by subject or proxy)
- Investigator's discretion
- A clinically significant hematologic adverse event leading to an interruption of treatment for greater than 28 days. Subjects will be allowed up to a 28-day delay in dosing for hematologic toxicity to resolve or for scheduling difficulties. If the investigator and GSK Medical Monitor conclude that the benefit: risk supports continued treatment of a subject who has had a > 28 day treatment delay, then the subject may continue therapy with the approval of the GSK Medical Monitor.
- A clinically significant non-hematologic adverse event leading to an interruption of treatment for greater than 14 days. Subjects will be allowed up to a 14-day delay in dosing for non-hematologic toxicity to resolve or for scheduling difficulties. If the investigator and GSK Medical Monitor conclude that the benefit: risk supports continued treatment of a subject who has had a > 14 day treatment delay, then the subject may continue therapy with the approval of the GSK Medical Monitor.
- Persistent G4 thrombocytopenia for 4 weeks not attributed to disease or requires platelet transfusions for bleeding in the absence of the disease.
- Intercurrent illness that prevents further administration of study treatment(s)
- Subject is lost to follow-up
- Study is closed or terminated.

The primary reason study treatment was permanently discontinued must be documented in the subject's medical records and electronic case report form (eCRF).

If the subject voluntarily discontinues from treatment due to toxicity, 'adverse event (AE)' will be recorded as the primary reason for permanent discontinuation on the electronic case report form (eCRF).

Once a subject has permanently discontinued from study treatment, the subject will not be allowed to be retreated.

All subjects who discontinue from study treatment will have safety assessments at the time of discontinuation and during post-study treatment follow-up as specified in Time and Events Table (see Section 7.1).

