4.2.5. Dose-Limiting Toxicity

An event will be considered a DLT if it occurs within the first 28 days of treatment (with exception of myelosuppression as stated below), and meets one of the following criteria unless it can be clearly established that the event is unrelated to treatment.

Subjects unable to receive at least 75% of scheduled doses within the DLT period for reasons other than toxicity (e.g., acute illness, disease progression) will not be evaluable

- Hematologic DLT: Myelosuppression (as defined by absolute neutrophil count (ANC) $<500/\mu\text{l}$ AND platelets $\leq 25,000/\mu\text{l}$) with bone marrow hypoplasia (cellularity $\leq 5\%$) without evidence of leukemia ($<5\%$ blasts) for ≥ 42 days after drug cessation.
- Grade ≥ 3 non-hematologic toxicity that is considered clinically significant and lasts >72 hours. Fatigue, asthenia, or nausea that respond to standard medical care within 72 hours and new electrolyte disturbance that respond within 24 hours are exceptions. In addition, electrolyte disturbances associated with underlying malignancy are not considered DLT.
- Grade 2 toxicity that in the judgment of the investigator and GSK Medical Monitor is dose-limiting.
- Treatment delay of ≥ 42 days due to unresolved toxicity (without evidence of leukemia ($<5\%$ blasts)).

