Thrombocytopenia if blasts <5%	Grade 4 (platelets $< 25,000/\text{mm}^3$) and/or any grade accompanied by severe bleeding related to thrombocytopenia	
If platelet count $< 25,000/\text{mm}^3$ but $\geq 10,000/\text{mm}^3$:
 
 1. Use clinical judgement to institute more frequent monitoring as necessary 2. Institute platelet transfusion as appropriate. 
If platelet count $< 10,000/\text{mm}^3$ (or $\leq 25,000/\text{mm}^3$ with accompanying fever, sepsis, or minor bleeding):
 
 1. Treatment may be held for up to 4 weeks and resume* as soon as count recovery has occurred (i.e., neutrophils ≥ 0.5 and platelets $\geq 25 \times 10^9/\text{L}$). Use clinical judgement to institute more frequent monitoring as necessary. 2. The treatment may be held for additional 1-2 weeks if the neutrophil and platelet counts do not recover after the initial 2 weeks. 3. After a total of 5-6 consecutive weeks, if there is no evidence of recovering blood counts, a repeat bone marrow examination should be performed

Toxicity	Dose Adjustment/ Stopping Criteria	Management Guidelines
		
during that period (approximately -35-42 days after drug cessation) to evaluate for the possibility of hematologic DLT.
 
4. If persistent for 6 weeks and not attributed to disease or requires platelet transfusions for bleeding in the absence of the disease, the subject will be withdrawn from the study.
 
*If treatment resumes, the dose and schedule may be adjusted based on platelet count, i.e., dose can be reduced by at least 25% increments up to two times.

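### Protocol 6.3 still permits a permanent stop at 4 weeks or after 28 days, before the 42-day hematologic DLT can be met, and Table 3 fixes no day-42 CBC for a subject so stopped

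*Protocol*

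**What the plan says.** Four places in the protocol bear on this.

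- **Section 4.2.5** defines the hematologic DLT in the item that opens "Hematologic DLT: Myelosuppression (as defined by absolute neutrophil count (ANC". It requires ANC below 500/µl and platelets at or below 25,000/µl, with marrow cellularity of 5% or less and blasts below 5%, for at least 42 days after drug cessation. A separate DLT item covers a treatment delay of at least 42 "days due to unresolved toxicity (without evidence of leukemia" on the marrow.
- **Section 4.8.3**, for thrombocytopenia with blasts below 5%, allows a hold of up to 4 weeks. It then says "The treatment may be held for additional 1-2 weeks" if counts have not recovered after the initial 2 weeks. After 5 to 6 weeks without recovery it asks for a repeat marrow, at roughly days 35 to 42 after cessation, to look for a hematologic DLT. Withdrawal follows "If persistent for 6 weeks and not attributed to disease".
- **Section 6.3** lists reasons for which treatment may be permanently discontinued. Two are hematologic: "Persistent G4 thrombocytopenia for 4 weeks not attributed to disease or requires platelet transfusions for bleeding in the absence of the disease", and "A clinically significant hematologic adverse event leading to an interruption of treatment for greater than 28 days". Going beyond 28 days needs Medical Monitor approval. It adds: "Once a subject has permanently discontinued from study treatment, the subject will not be allowed to be retreated". Subjects who discontinue "will have safety assessments at the time of discontinuation and during post-study treatment follow-up as specified in Time and Events Table".
- **Table 3 (Section 7.1)** has a CBC at the End of Treatment visit, followed only by survival telephone calls. The disease-assessment marrow row has no End of Treatment entry. Section 7 places that visit within 14 days of the last dose.

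The SAP lists DLTs among the Part 1 primary endpoints and adds no rule on this point.

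**The concern.** Sections 4.8.3 and 6.3 describe the same event in almost the same words, one with a 6-week limit and the other with a 4-week limit. The amendment log explains how this could arise: Amendment 5 moved the DLT criterion from 28 to 42 days and the 4.8.3 withdrawal limit from 4 to 6 weeks. The point itself rests on the current text, in which 6.3 stands at 4 weeks and 28 days.

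A subject with unresolved aplasia can therefore be stopped for good before the DLT definition can be satisfied, and no fixed assessment follows at the time when it could be. DLTs are a Part 1 primary endpoint and the data on which the dose-escalation model is updated. The evaluability and replacement rules in 4.2.1, 4.2.2 and 4.2.5 remove only subjects who miss doses for reasons other than toxicity. A subject stopped for aplasia is not removed by them, and the plan does not say how that subject is classified.

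**Working it through.** No sample size, power or error rate is involved. The check is day arithmetic on the stated limits, followed by a comparison of the provisions.

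**1. Difference between the limits.** 6.3 uses 28 days; 4.2.5 and 4.8.3 use 42 days (6 weeks). 42 − 28 = 14 days.

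**2. Interruption limb of 6.3.** The interruption runs from the last dose, as the DLT clock does. More than 28 days means that a stop is permitted from day 29. Days before day 42 on which a subject can be stopped: 41 − 29 + 1 = 13.

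**3. Thrombocytopenia limb of 6.3.** The section does not say when its 4 weeks begin, and thrombocytopenia may start before or after the last dose. No gap is computed for this limb.

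**4. Last fixed CBC for a stopped subject.**
- Stopped on days 29 to 41 under the interruption limb: the 14-day End of Treatment window has passed, but 6.3 requires an assessment at discontinuation. That falls between 42 − 41 = 1 and 42 − 29 = 13 days short of day 42.
- Stopped at once for another reason: the End of Treatment visit is at day 14 or earlier, at least 42 − 14 = 28 days short.

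Neither route fixes a CBC at day 42.

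**5. Do other provisions supply it?**

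| Provision | What it gives | What it leaves open |
|---|---|---|
| 7.3.7 | Significantly abnormal labs on study, or within 30 days of the last dose, should be repeated until normal or baseline | No interval. If recovery does not come in a period the investigator finds reasonable, the duty becomes finding the cause and notifying the sponsor. Eligibility sets no minimum ANC or platelet count, so baseline may itself be very low |
| 8.5 | Ongoing AEs are followed after discontinuation | May end at stabilization, which unchanging aplasia could satisfy |
| 4.8.3 marrow | About days 35 to 42 after cessation, aimed at this DLT | Sits in the treatment-hold instructions. If done on days 35 to 41 it cannot alone show 42 days, and no rule says how it counts |

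**6. Does the treatment-delay DLT catch the subject?** It catches a subject still on hold at day 42, who also keeps the scheduled Table 3 CBCs. It does not clearly catch one already stopped: 6.3 bars retreatment, so a permanent stop is hard to call a delay.

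**The case against.** A reader might infer that an early-stopped subject has no required blood count or marrow follow-up at all. The documents do not support that. Section 7.3.7 keeps abnormal labs under repeat, 8.5 keeps ongoing events under follow-up, and the 4.8.3 marrow is timed from drug cessation, with nothing that expressly excludes a stopped subject. This much of the objection stands. What is missing is a fixed day-42 CBC and a statement that the marrow applies after a permanent stop.

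It can also be said that the two sections do not strictly contradict each other. Section 6.3 is permissive and 4.8.3 is mandatory, so a site can obey both: it may stop after 4 weeks and must withdraw at 6. Medical Monitor approval also allows continuation past 28 days. That is right, and it is why the point is about an unaligned limit and not an impossible instruction. The permission still opens the 13-day gap.

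A third objection is that aligning 6.3 alone would not close the gap, because stops for investigator discretion, subject request or intercurrent illness would remain. This also stands, and it shapes the fix: the follow-up requirement has to apply whatever the reason for stopping.

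**Conclusion.** The point holds as a minor one. Section 6.3 was not brought into line with the 6-week and 42-day limits used elsewhere, and for a Part 1 subject permanently stopped before day 42 the plan neither fixes the CBC needed to establish a hematologic DLT nor says how the case is classified. On the interruption limb the gap is 13 days, counting the interruption from the last dose.

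The affected group is very small. Low ANC, low platelets, a hypoplastic marrow and blasts below 5% must coincide with an optional early stop. The documents give no basis for estimating how often this would happen.

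A reader might go further and infer that a wrong dose escalation would follow. The documents do not support that. The dose-escalation committee reviews all adverse events, including toxicities that are not DLTs, and can halt or reduce escalation (4.2.1). In the monotherapy arm, escalation requires data from at least one subject who has completed the 4-week window, so a DLT established 42 days after cessation could arrive after the decision even with perfect follow-up. The supported consequence is a DLT that may go unestablished in the endpoint and in the model's data.

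**What to change.** 1. In 6.3, change the 4-week Grade 4 thrombocytopenia limit and the 28-day hematologic interruption limit to match the 6-week/42-day rule in 4.8.3.
2. In Part 1, require CBCs through day 42 after the last dose for any subject with unresolved cytopenia and blasts below 5%, whatever the reason for stopping, unless consent is withdrawn. Add this to Table 3.
3. In 4.8.3, state that the repeat marrow and the DLT evaluation also apply to permanently stopped subjects. State that a hypoplastic, leukemia-free marrow at days 35 to 41, together with ANC below 500/µl and platelets at or below 25,000/µl on day 42, counts as a hematologic DLT.

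The cost is protocol wording and a few extra CBCs in a very small subgroup, with DLT status known slightly later for those subjects. No marrow is added beyond the one 4.8.3 already calls for. For a subject stopped before day 35, item 3 makes explicit a procedure that the current text leaves uncertain. The counting rule keeps the clinical value of a marrow taken before day 42.

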6.4. Study Completion

The study will be considered completed, having met the study objectives, when 80% or more subjects in Part 2 have withdrawn from the study. At such time, subjects who have not been permanently withdrawn from study treatment and continue to benefit will be offered the opportunity to continue treatment in a separate rollover protocol.

Per the EU Clinical Trial Directive, the end of the study is defined as the last subject's last visit.

6.5. Treatment after the End of the Study

The investigator is responsible for ensuring that consideration has been given for the post-study care of the subject's medical condition whether or not GSK is providing specific post-study treatment.

7. STUDY ASSESSMENTS AND PROCEDURES

A signed, written informed consent form must be obtained from the subject prior to any study-specific procedures or assessments being performed.

The timing of each assessment is listed in the Time and Events Table (Section 7.1). The timing and number of the planned study assessments may be altered during the course of the study based on newly available data (e.g. to obtain data closer to the time of peak plasma concentrations) to ensure appropriate monitoring for the following assessments: safety, PK, PD/biomarker assessments. The change in timing or addition of time points for any of the planned study assessments listed above must be approved and documented by GSK, but this will not constitute a protocol amendment. The institutional review board (IRB) or ethics committee (EC) will be informed of any safety issues that require alteration of the safety monitoring scheme.

Whenever vital signs, 12-lead ECGs and blood draws are scheduled for the same nominal time, the assessments should occur in the following order: 12-lead ECGs, vital signs, blood draws.

If the blood draw is done first, there should be at least 15 minute interval before the vital signs and 12-lead ECGs measurements are taken.

On clinic days, study drug should be taken in the clinic after all the safety procedures (including CBC) and blood sampling for PK/PD, if applicable, are completed.

Detailed procedures for obtaining each assessment are provided in the Study Procedures Manual (SPM).

Visit Window

Informed consent should be signed within 35 days prior to dosing.

Baseline disease assessment should be completed within **21 days** prior to dosing start.

ECHO/MUGA should be completed within **35 days** prior to dosing start.

Pregnancy testing should be completed **7 days** prior to dosing start and all other screening assessments should be completed within **14 days** prior to dosing start.

Visits in the first 4 weeks will be allowed ± 1 day window. Bone marrow on Day 15 can be done between Day 8 and Day 21.

Visits beyond the first 4 weeks will have ± 3 days window.

The End of Treatment visit should be completed within **14 days** from the last dose.

Time Window for PK sampling

0.25, 0.5, 1 and 1.5 hours post dose sampling: ± 5 minutes

2, 3, 4 hours post dose sampling: ± 10 minutes

6, 8, and 10 hours post dose sampling: ± 30 minutes

24 hours post dose sampling: ± 1 hour and should be done before the next dose administration.

48 and 72 hours post dose sampling: ± 3 hours. The 72 hour sampling should be done before the next dose administration.

7.1. Time and Events Table(s)

This section consists of the Time and Events Table(s) and supplemental footnotes to describe assessment windows and sequencing of study-specific assessments and procedures.

Table 3 Time and Events, Part 1 Dose Escalation

	SCR	First Treatment Phase (28 days)										Continuation Phase	EOT	SFU Q12W
		D 1	D 2	D 4	D 8	D 11	D 15	D 16	D 18	D22	D25			
Office Visit	X	X	X	X	X	X	X	X	X	X	X		X	
Informed consent	X													
Demography	X													
Medical history	X													
Disease characteristics	X													
Review subject dosing diary				X	X		X					every 4 wks	X	
Study Drug Dosing ¹⁴		< ----- Daily or per dosing schedule ----- >												
Study Drug Dispensing		X										every 4 wks		
Complete physical exam	X												X	
Brief physical exam		X ¹¹			X							every 4 wks		
Montreal Cognitive Assessment	X	X			X		X			X		Wk 4 and every 4 wks		
Performance status	X	X ¹¹			X							every 4 wks	X	
Vital Signs	X	X ¹¹		X	X		X					every 4 wks	X	
Height and weight ¹⁰	X	X ¹¹			X							every 4 wks	X	
ECHO or MUGA	X												x	
12-lead ECGs	X	X			X							every 4 wks	X	
HIV, HBsAg and HCV Ab testing	X													
CBC	X	X ¹¹		X	X	X	X		X	X	X	Every week x 4(wk 4-7), wk 8 then every 4 wks ¹⁶	X	
Chemistry Panel including liver function tests	X			X ²²	X	X ²²	X			X		every 4 wks	X	

	SCR	First Treatment Phase (28 days)										Continuation Phase	EOT	SFU Q12W	
		D 1	D 2	D 4	D 8	D 11	D 15	D 16	D 18	D22	D25				
Fasting Lipid panel (triglyceride, cholesterol) ²²	X				X		X				X		every 4 wks		
Coagulation Panel (PT, PTT, INR, fibrinogen)	X				X		X				X		every 4 wks	X	
Vitamin B12, TSH, Free T4 or Free T3 ²³	X														
Fetal hemoglobin (Hgb F)		X			X		X								
Pregnancy test ⁸	X												every 4 wks	X	
PK Blood samples		X ¹	X ¹	X ⁴	X ²		X ³	X ³			X ⁴		Every week x 4 (wk 4-7), wk 8, then every 4 wks ⁴		
Blood samples for PD ^{6, 21} (peripheral blood)	X		X	X	X	bone marrow day ⁶						Wk 4, between Wk 6- 8, Wk 12 and then every 12 wks.	X		
Blood samples for exploratory studies ^{6, 21} (peripheral blood)	X			X											
Bone marrow aspirate for PD ²¹	X ⁷					X ¹⁸						Wk 4, between Wk 6- 8, Wk 12 and then every 12 wks	X ¹⁷		
Bone marrow aspirate for exploratory studies ²¹	X ⁷					X ¹⁸						Wk 4, between Wk 6- 8, Wk 12 and then every 12 wks.	X ¹⁷		
Blood smear to measure blasts	X			X	X		X						Every week x 4 (wk 4-7), Wk8, then every 4 wks		
Bone marrow aspirate/biopsy for disease assessment ^{24, 25}	X ²⁰					X ¹⁸						Wk 4, between Wk 6- 8 ¹⁹ , Wk 12 and then every 12 wks.			
Telephone call for survival status ²⁶														X	
PGX sample (buccal swab)	X														
PK blood sample on bone marrow day ¹⁵						X (bone marrow day)						Wk 4, between Wk 6- 8, Wk 12 and then every 12 wks			
Transfusion Assessment ¹³	X				X		X				X		Every week x 4 (wk 4-7), wk 8, then every 4 wks		

	SCR	First Treatment Phase (28 days)										Continuation Phase	EOT	SFU Q12W
		D 1	D 2	D 4	D 8	D 11	D 15	D 16	D 18	D22	D25			
Adverse Events		continuous												
Con Meds		continuous												
Highest Dose in PK/PD expansion cohort ONLY														
Blood for metabolite evaluation		X ⁹	X ⁹				X ⁹	X ⁹						
Urine for metabolite evaluation		X ^{5, 12}	X ⁵				X ⁵	X ⁵						
Urine for PK		X ^{5, 12}	X ⁵				X ⁵	X ⁵						

1. A blood sample will be collected for PK analysis on D1 at following time points: pre-dose, 0.25, 0.5, 1, 1.5, 2, 3, 4, 6, 8, 10, and 24 hrs post dose. In the combination cohort, a blood sample for ATRA PK analysis will be also collected at the same time points except for the 0.25, 10 and 24 hour sample. Additional samples may be collected at 48 and 72 hrs post dose in subjects not receiving a dose on Days 2 and 3 to better characterize the terminal half-life of GSK2879552, if needed.
2. A blood sample will be collected for PK analysis on D8 at following time points: pre-dose, 0.5, 3 hrs post dose. In the combination cohort, a blood sample for ATRA PK analysis will be also collected at the same time points.
3. A blood sample will be collected for PK analysis on D15 at following time points: pre-dose, 0.25, 0.5, 1, 1.5, 2, 3, 4, 6, 8, 10, and 24 hrs post dose. In the combination cohort, a blood sample for ATRA PK analysis will be also collected at the same time points except for the 0.25, 10 and 24 hour sample.
4. PK blood sample should be taken pre-dose around the same time as CBC. If the dose has been modified since the last PK sample and an unscheduled CBC sample is taken, a PK sample should be obtained together with the first unscheduled CBC sample. PK sample will not be collected beyond week 48.
5. On Days 1 and 15, 24hr urine will be collected in the highest dose cohort in PK/PD expansion cohorts starting from post-dose on Day 1 and 15, and for 24 hours, i.e., until dosing on Days 2 and 16, respectively. The 24hr urine will be measured and samples collected for PK and metabolite evaluation.
6. Blood samples for PD and exploratory studies should be collected pre-dose.
7. A fresh bone marrow aspirate is requested from all subjects. This requirement is mandatory for all subjects participating in the PK-PD cohorts.
8. For women of child bearing potential only. Serum pregnancy test is required for screening and EOT visits. Urine pregnancy test is adequate during study visits.
9. Additional samples will be collected for metabolite evaluation in the highest dose cohort in PK/PD expansion cohorts, in at least 3 subjects. The plasma samples will be collected at following time points on Days 1 and 15: pre-dose, 0.25, 0.5, 1, 1.5, 2, 3, 4, 6, 8, 10, and 24 hrs post dose
10. Height will be measured at screening only
11. These procedures do not need to be repeated on Day 1, if the screening visit was within 3 days and they were performed at screening.
12. A urine sample will be collected for PK analysis and metabolite evaluation at pre-dose on D1 in the highest dose cohort in PK/PD expansion cohorts.
13. Platelet and blood transfusions to be assessed at designated visits and summarized per unit on a weekly cumulative basis.
14. On clinic days, study drug should be taken in the clinic after safety procedures including CBC and PK/PD samplings, if applicable, are completed.
15. PK blood sample should be collected pre-dose on the day of bone marrow biopsy. This sample should be collected if the bone marrow biopsy was performed on the non-planned visit days and the "PK blood sample" was not collected,

16. Twice weekly CBC monitoring may continue per institutional guidelines.
17. Bone marrow aspirate at the time of progression is optional for all subjects.
18. Between D8 and D21, timing to be optimized based on emerging data.
19. The assessment of response should occur between 1 – 4 weeks of count recovery (ANC > 1000/ μ l and platelets > 100,000/ μ l). Subjects should be off cytokine support (GCSF or GMCSF) for a minimum of 7 days before obtaining bone marrow to document remission.
20. Baseline disease assessment should be completed within 21 days prior to dosing start. Cytogenetics testing should be performed as part of disease assessment at baseline. Cytomorphology is the preferred method to determine bone marrow blast counts. However, if a bone marrow aspirate cannot be obtained for cytomorphology review, a bone marrow biopsy is strongly recommended to determine the bone marrow blast count.
21. In PK/PD expansion cohorts, PD and/or exploratory sample (peripheral blood and BMA) collection may be stopped earlier at the sponsor's discretion.
22. ATRA combination arm only.
23. Free T3 to be tested only when clinically indicated
24. At any time point in the study, if a bone marrow aspirate is found to be hemodilute (no spicules) or uninterpretable, then a bone marrow biopsy is strongly recommended to be collected at the next disease assessment time point in addition to the aspirate to ensure the conduct of a disease assessment.
25. BM slides may be evaluated for changes in morphology.
26. The Survival FU visit should be completed every 12 weeks after documented disease progression (or after initiation of another anticancer treatment). Subjects should be contacted every 12 weeks (\pm 2 weeks) until death occurs.

Table 4 Time and Events Table: Part 2 – Expansion Cohort

	SCR	First Treatment Phase (28 days)								Continuation Phase	EOT	SFU Q12W
		D 1	D4	D 8	D11	D 15	D18	D22	D25			
Office Visit	X	X	X	X	X	X	X	X	X	every 4 wks	X	
Informed consent	X											
Demography	X											
Medical history	X											
Disease characteristics	X											
Study Drug Dosing ⁹		< ----- Daily or per dosing schedule ----- >										
Review subject dosing diary				X		X				every 4 wks	X	
Study Drug Dispensing		X								every 4 wks		
Complete physical exam	X										X	
Brief physical exam		X ⁷		X						every 4 wks		
Montreal Cognitive Assessment	X	X		X		X		X		Wk 4 and every 4 wks		
ECOG PS	X	X ⁷		X						every 4 wks	X	
Vital Signs	X	X ⁷		X		X				every 4 wks	X	
Height and weight ⁶	X	X ⁷		X						every 4 wks	X	
ECHO/MUGA	X											
12-lead ECGs	X	X ⁷		X						every 4 wks	X	
HIV, HBsAg and HCV Ab testing	X											
CBC	X	X ⁷	X	X	X	X	X	X	X	Weekly x 4 wks (Wk 4-7), Wk 8 and every 4 wks ¹²	X	
Chemistry Panel including LFT	X		X ¹⁸	X	X ¹⁸	X		X		every 4 wks	X	
Fasting Lipid panel (triglyceride, cholesterol) ¹⁸	X			X		X		X		Every 4 wks		
Coagulation Panel including PT, PTT, INR, fibrinogen	X			X		x		X		every 4 wks	X	

	SCR	First Treatment Phase (28 days)								Continuation Phase	EOT	SFU Q12W
		D 1	D4	D 8	D11	D 15	D18	D22	D25			
Vitamin B12, TSH, Free T4 or Free T3 ²⁰	X											
PK Blood samples		X ¹	X ⁸	X ⁸		X ²				Weekly x 4 wks (Wk 4-7), Wk 8 and every 4 wks ⁸		
Fetal hemoglobin (Hgb F)		X		X		X						
Pregnancy test ⁴	X									every 4 wks	X	
Blood samples for PD (peripheral blood) ^{3, 19}	X		X	X	bone marrow day ¹⁴					Wk 4, between Wk 6-8, Wk 12, then every 12 wks	X	
Blood samples for exploratory studies ^{3, 19} (peripheral blood)	X		X									
Bone marrow aspirate for PD ¹⁹	X					X ¹⁴				Wk 4, between Wk 6-8, Wk 12, then every 12 wks	X ⁵	
Bone marrow aspirate for exploratory studies ¹⁹	X ¹¹					X ¹⁴				Wk 4, between Wk 6-8, Wk 12, then every 12 wks	X ⁵	
Blood smear to measure blasts	X			X		X				Every week x 4 (Wk 4-7), Wk 8 then every 4 wks		
Bone marrow aspirate /biopsy for disease assessment ^{21, 22}	X ¹⁶					X ¹⁴				Wk 4, between Wk 6-8 ¹³ , Wk 12, then every 12 wks		
Telephone call for survival status ²³												X
PGX samples (buccal swab)	X											
PK blood sample on bone marrow day ¹⁵					X (on bone marrow day)					Wk 4, between Wk 6- 8, Wk 12, then every 12 wks.		
Transfusion Assessment ¹⁰	X			X		X		X		Every week x 4 (wk 4-7), Wk 8, then every 4 wks		
Adverse Events		Continuous										
Con Meds		Continuous										

1. A blood sample will be collected for PK analysis on D1 at pre-dose, 0.5, and 3 hrs post dose. . In the combination cohort, a blood sample for ATRA PK analysis will be collected at the same time points.
2. A blood sample will be collected for PK analysis on D15 at pre-dose, between 0.5 to 1 hour, and between 4 and 6 hours. In the combination cohort, a blood sample for ATRA PK analysis will be collected at the same time points.

3. Blood samples for PD, exploratory studies should be collected pre-dose.
4. For women of child bearing potential only. Serum pregnancy test is required for screening and EOT visits. Urine pregnancy test is adequate during study visits.
5. Bone marrow aspirate at the time of progression is optional for all subjects.
6. Height will be measured at screening only
7. These procedures do not need to be repeated on Day 1, if the screening visit was within 3 days and they were performed at screening.
8. PK blood sample should be taken pre-dose around the same time as CBC. PK sample will not be collected beyond 48 weeks.
9. On clinic days, study drug should be taken in the clinic after safety procedures including CBC and PK/PD samplings, if applicable are completed.
10. Platelet and blood transfusions to be assessed at designated visits and summarized per unit on a weekly cumulative basis
11. A fresh bone marrow aspirate at baseline is required in Part 2
12. Twice weekly CBC monitoring may continue per institutional guidelines.
13. The assessment of response should occur between 1 – 4 weeks of count recovery (ANC > 1000/ μ l and platelets > 100,000/ μ l). Subjects should be off cytokine support (GCSF or GMCSF) for a minimum of 7 days before obtaining bone marrow to document remission.
14. Between D8 and D21, timing to be optimized based on emerging data.
15. PK blood sample should be collected prior to dosing on biopsy days. This sample should be collected if the bone marrow biopsy was performed on the non-planned visit days and the “PK blood sample” was not collected within the time frame
16. Baseline disease assessment should be completed within 21 days prior to dosing start. Cytogenetics testing should be performed as part of disease assessment at baseline. Cytomorphology is the preferred method to determine bone marrow blast counts. However, if a bone marrow aspirate cannot be obtained for cytomorphology review, a bone marrow biopsy is strongly recommended to determine the bone marrow blast count.
17. Sample should be collected at pre-dose on the day of bone marrow aspirate collection.
18. ATRA combination only
19. PD and/or exploratory sample (peripheral blood and BMA) collection may be stopped earlier at the sponsor’s discretion
20. Free T3 to be tested only when clinically indicated
21. At any time point in the study, if a bone marrow aspirate is found to be hemodilute (no spicules) or uninterpretable, then a bone marrow biopsy is strongly recommended to be collected at the next disease assessment time point in addition to the aspirate to ensure the conduct of a disease assessment.
22. BM slides may be evaluated for changes in morphology.
23. The Survival FU visit should be completed every 12 weeks after documented disease progression (or after initiation of another anticancer treatment). Subjects should be contacted every 12 weeks (\pm 2 weeks) until death occurs.

